### 2.3.2 Protocol Deviations

Subjects with any protocol deviations will be summarized by type for each country and overall.

### 2.3.3 Demographic Characteristics

Age and body mass index will be summarized as continuous variables.

Gender, race, ethnicity, Fitzpatrick Skin Type (FST), baseline MLFS (upper and lower lip) and childbearing potential will be summarized as categorical variables.

Demographics will be summarized by country and overall.

### 2.3.4 Medical History, Medications, and Procedures

Prior and concomitant medications and vaccines will be coded using the World Health Organization Drug Dictionary (WHODD). Medical history, prior cosmetic treatments/procedures, and concomitant procedures/treatments will be coded according to the Medical Dictionary for Regulatory Activities (MedDRA).

Prior medications/procedures are the medications/procedures with stop dates prior to first study treatment session. Medications/procedures after the first study treatment session will be considered concomitant.

Subjects reporting medical history, prior cosmetic treatments/procedures, and concomitant procedures/treatments will be summarized by System Organ Class (SOC) and Preferred Term (PT).

Subjects reporting prior and concomitant medications will be summarized separately, by WHODD Anatomical Therapeutic Chemical (ATC) Class Level 3 (if Level 3 is not available, the highest class available will be used) and WHODD preferred name.

## 2.4 Effectiveness Analysis

### 2.4.1 Datasets Analyzed

The MITT population is primary for all effectiveness analyses. The MITT population will be split into two subgroups for analysis by country.

### 2.4.2 Handling of Missing Data

Number of missing values will be summarized and reported as appropriate.

All effectiveness endpoints will be evaluated based on observed cases in the MITT population. Sensitivity analyses will be performed for the MLFS. The first sensitivity analysis will replace all missing values with the most negative answer (1). The second sensitivity analysis will replace all missing values with the most positive answer (5). MLFS tables will be repeated for both sensitivity analyses.

### 2.4.3 Primary Effectiveness Analysis

#### 2.4.3.1 Medicis Lip Fullness Scale

MLFS will be presented with number of subjects and percentage for each category of the scale. The proportion of responders based on MLFS (defined as at least 1-point improvement from baseline) as assessed by the investigator at weeks 8, 16, 24, 32, 40, and 48 after last injection will be calculated and presented with their 95% confidence intervals (calculated via Clopper-Pearson). Response rates will be calculated for the upper and lower lip separately as well as for both lips combined. A bar plot of the percentage of responders for each upper lip, lower lip and combined by visit also will be produced for each.

In addition, the change from baseline at weeks 8, 16, 24, 32, 40, and 48 after last injection will be calculated for the upper and lower lip separately. The number of subjects and percentage for each point change (+4, +3, +2, etc.) from baseline will be presented.

#### 2.4.3.2 Wrinkle Assessment Scale

WAS will be presented with number of subjects and percentage for each category of the scale. The proportion of responders based on the WAS (i.e., at least a one point improvement from the investigator baseline assessment of the upper perioral rhytids and oral commissures at weeks 8, 16, 24, 32, 40, and 48) will be calculated and presented along with their 95% confidence intervals (calculated via Clopper-Pearson). A bar plot of the percentage of responders for each upper perioral rhytids and oral commissures by visit also will be produced for each.

In addition, the change from baseline at weeks 8, 16, 24 32, 40, and 48 after last injection will be calculated. The number of subjects and percentage for each point change (+3, +2, +1, 0, etc.) from baseline will be presented.

#### 2.4.3.3 Global Aesthetic Improvement Scale

GAIS will be presented with number of subjects and percentage for each category of the scale. For the GAIS, response rate is defined as a subject with a rating of at least “improved”. The response rates based on the GAIS as assessed by the investigator and the subject, respectively, at Week 8, 16, 24, 32, 40, and 48 after last injection will be calculated and presented along with their 95% confidence intervals (calculated via Clopper-Pearson). A bar plot of the percentage of responders (at least “Improved”) by visit also will be produced for each evaluator type (investigator and subject).

CCI

[REDACTED]

### 2.5 Safety Analysis

Safety endpoints will be summarized using descriptive statistics based on the safety population using observed cases. There are no planned inferential statistical analyses of safety endpoints.

#### 2.5.1 Treatment Administration and Procedural Anesthetics

Treatment administration endpoints that will be summarized by treatment session, treatment location and overall include (but are not limited to): injection volume, injection method, and depth of injection.

The number of subjects with any procedural anesthetics will be summarized by anesthetic type.

#### 2.5.2 Adverse Events (AEs)

All AEs will be coded according to MedDRA and summarized by System Organ Class (SOC), and Preferred Term (PT), including number of subjects with at least one event, associated percentage, and number of events.

For subject counts, a subject will only be counted once per SOC and once per PT in cases where multiple events are reported for a subject within SOC or PT. For event counts, subjects with multiple events in a category will be counted for each event.

The number of subjects with AEs related to study product or study product injection procedure, as well as the number of events, will be presented by SOC, PT, and maximum intensity. Action taken for related AEs will also be summarized by SOC and PT using number of events. Serious AEs will be listed. AEs related to study product or injection procedure with late onset (> 21 days after most recent treatment session) will be listed.

AEs unrelated to study product or injection procedure will be summarized by SOC, PT, and maximum intensity.

For AEs related to study product or study product injection procedure, the number of days to onset and the duration of event will be summarized by SOC and PT using mean, standard deviation, median, minimum, and maximum. Days to onset of an AE will be derived as the start date minus the date of most recent treatment session. Duration of an AE will be derived as the stop date minus the start date + 1.

For the purpose of deriving days to onset and duration, the following date imputation rules will be used.

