#### 3.4.1 Visit 1: Screening (Day -30 to Day 1)

The screening visit and baseline visit (Day 1/Treatment) may be performed on the same day.

The following activities and screening assessments will be performed within 30 days prior to baseline.

- Obtain informed consent prior to conducting any study specific procedure.

- Record the subject's medical history (including any prior dermatological procedures or implants).
- Record the subject's prior and concomitant medications/procedures.
- Obtain demographic data: date of birth, height, weight, gender, ethnicity, race, and Fitzpatrick Skin Type (FST). For determination of the FST, see [Table 2](#) below.
- Perform UPT for females of childbearing potential.
- Investigator assessment of lip fullness using the MLFS.
- For subjects in the US: Investigator assessment of perioral rhytid wrinkle severity using the WAS.

CCI

- Evaluate the subject for pre-treatment AEs.
- Assess eligibility (inclusion and exclusion criteria), including confirmation that subject is of full Chinese descent.
- Schedule the baseline visit (Day 1/Treatment), if performed on a different day than the screening visit.

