### 3.4.2 Visit 2: Baseline/Day 1 (Treatment)

If the screening and baseline visits are not performed on the same day, the following procedures should be repeated:

- Record the subject's medical history (including any prior dermatological procedures or implants).
- Record the subject's prior and concomitant medications/procedures.
- Perform UPT for females of childbearing potential.
- Investigator assessment of lip fullness using the MLFS.
- For subjects in the US: Investigator assessment of perioral rhytid wrinkle severity using the WAS.

CCI

- Interview and assess for pre-treatment AEs.
- Re-confirm eligibility.

The following procedures should be performed at the baseline visit only:

CCI

- Obtain pre-treatment photography.
- Investigator to treat the subject with *Restylane Kysse* (upper and lower lips, and perioral rhytids, if eligible and agreed upon by the investigator and subject).
- Evaluate the subject for post-treatment AEs.
- Record post-treatment concomitant medications/procedures
- Evaluate for device deficiencies.

CCI

- Schedule the Week 2 visit (Visit 3).

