##### 7.1.1.1 Reporting of Adverse Events

Adverse event reporting on each subject shall start after signing of the informed consent at screening. The reporting shall continue during each follow-up visit (including telephone contacts and extra visits between planned visits) until the last scheduled visit in the study (i.e. Visit 10/Week 48 after last injection).

All AEs, non-serious as well as serious, are to be reported as an AE in the eCRF.

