### 2.2.2 Safety Population

The Safety population includes all subjects who were treated with *Restylane Kysse* in at least one lip, and will be analyzed according to the treatment actually received. All safety data will be summarized descriptively based on the Safety population.

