#### End Date

- If end date is completely missing, it will be assumed that the AE is still ongoing and will not be imputed.
- If the end date is missing the day, the last of the month will be used (i.e. UNK-JAN-2022 becomes 31-JAN-2022)
- If the end date is missing the month, the subsequent month after the start date will be used.
- If the end date is missing the year, the year of first treatment will be used, provided the imputed date is after the start date; otherwise, the subsequent year after start date will be used.

Adverse events with a completely missing start date will be considered treatment-emergent unless the event has a stop date prior to the date of the first dose of study drug. All AEs will be listed by treatment and subject. Dates will be presented as collected in the listings.

In addition, a summary of all AEs will be provided, which will include (but is not limited to):

- number of subjects with at least one AE and number of events (in total as well as serious AEs),
- number of subjects with at least one related AE and number of events (in total as well as serious AEs),
- number of subjects with at least one unrelated AE and number of events (in total as well as serious AEs),

GALDERMA EST. 1981	Title 05DF2007 Statistical Analysis Plan (SAP)	CC I [REDACTED]
-----------------------	--	--------------------

- number of subjects who did not have an AE.

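### The SAP's all-AE, unrelated-AE and overall AE summaries state no onset limit, so AEs before the first injection would count, and the lip findings are planned only as by-visit frequencies (minor)

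*SAP*

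**What the plan says.** **Collection.** Protocol 7.1.1.1: "Adverse event reporting on each subject shall start after signing of the informed consent at screening". The visit descriptions ask for such events directly. Screening (Protocol 3.4.1) has "Evaluate the subject for pre-treatment AEs". Baseline (Protocol 3.4.2), when held on a different day, has "Interview and assess for pre-treatment AEs". Screening may take place up to 30 days before baseline or on the same day.

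**Population.** SAP 2.2.2: "The Safety population includes all subjects who were treated with" the product in at least one lip. This selects subjects, not events.

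**AE tables.** SAP 2.5.2 plans an all-AE table ("All AEs will be coded according to MedDRA and summarized by System Organ Class (SOC), and Preferred Term (PT", with subject and event counts) and a further table: "AEs unrelated to study product or injection procedure will be summarized by SOC, PT, and maximum intensity". Its overall summary includes the "number of subjects who did not have an AE". None of the three states an onset limit.

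**Treatment-emergent.** The readable SAP uses the term once, under End Date in 2.5.2: "Adverse events with a completely missing start date will be considered treatment-emergent unless the event has a stop date prior to" the first dose. No described table is restricted to that class, and AEs with known dates are given no definition.

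**Lip findings.** SAP 1.2.2 has palpation, texture, symmetry, movement, function and sensation assessed at baseline and at each clinic follow-up. SAP 2.5.4 plans only frequency tables for each visit.

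**The concern.** Total and unrelated AE counts would mix events from before and after exposure, and the tables would not show how many came before. A cold during screening in a subject who is later treated would count as an AE and would take that subject out of the no-AE row. The lone rule on treatment-emergent events suggests that a restriction may have been intended. It has no effect on any table described.

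For the lips, separate frequencies at each visit let a new finding in one subject be offset by a resolved finding in another. The study has no control arm and no planned safety inference (SAP 2.5), so the tabulated counts are the safety result. Protocol 1.4 says the study is meant to support a marketing application.

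**Working it through.** The documents give no figure on this point, so there is none to reproduce. The check sizes the effect.

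**1. Share of AE observation time before treatment.** AE reporting ends 48 weeks after the last injection. Counted from the first injection, that is 48 × 7 = 336 days without a touch-up, or 52 × 7 = 364 days with a touch-up at Week 4. For a screening interval of d days the share is d/(d + 336) or d/(d + 364).

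| d (days) | No touch-up | Touch-up |
|---|---|---|
| 0 | 0% | 0% |
| 7 | 7/343 = 2.0% | 7/371 = 1.9% |
| 14 | 14/350 = 4.0% | 14/378 = 3.7% |
| 30 | 30/366 = 8.2% | 30/394 = 7.6% |

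**2. Pre-treatment events in the totals.** The documents give no background AE rate. Assume a constant unrelated-AE rate r of 0.25 to 1.0 per person-year and 50 subjects with the same screening interval. Events = 50 × r × d/365.

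- d = 0: 0 events.
- d = 14: 0.48 (r = 0.25) to 1.92 (r = 1.0).
- d = 30: 1.03 (r = 0.25) to 4.11 (r = 1.0).

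**3. Subjects who leave the no-AE row only because of a screening AE.** Without touch-up, and with no related AEs, the expected number is 50 × (1 − exp(−r·d/365)) × exp(−r·336/365).

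- d = 30: 0.81 (r = 0.25), 1.27 (r = 0.5), 1.57 (r = 1.0).
- d = 14: 0.38, 0.60, 0.75 for the same rates.
- The maximum over all constant rates at d = 30 is 1.57, at r = 1.04. With 364 days of follow-up it is 1.46.

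A subject with a related AE is outside the no-AE row anyway. If a share p has one, independently of unrelated AEs, multiply by (1 − p):

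- d = 30: 0.61 to 1.18 at p = 25%, 0.40 to 0.79 at p = 50%, 0.20 to 0.39 at p = 75%.
- d = 14: 0.19 to 0.37 at p = 50%.

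As a cross-check, start instead from an assumed incidence q of at least one unrelated AE during 336 days of follow-up. Adding 30 days at the same hazard raises it by 1 − (1 − q)^(366/336) − q. This is 0.8 percentage points at q = 10% and peaks at 3.1 points near q = 62%, which is again about 1.6 of 50 subjects.

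**4. Related AEs.** Protocol 7.1.1.2.2 calls an AE related only if the investigator sees a reasonable possibility that the product or the injection procedure caused it. An event that began before the first injection cannot reasonably meet that test, so the effect here is essentially zero.

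**5. Lip tables.** With a subjects abnormal at baseline and b at a later visit, out of 50, the number newly abnormal lies between max(0, b − a) and min(b, 50 − a). The counts below are assumed, for illustration.

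| a | b | Newly abnormal |
|---|---|---|
| 3 | 3 | 0 to 3 |
| 2 | 3 | 1 to 3 |
| 1 | 3 | 2 to 3 |
| 0 | 3 | exactly 3 |

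Information is lost only when some subject is abnormal at baseline.

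**The case against.** The best defence is that this is a choice and not an error. Protocol 9.6 states no onset limit either, and the SAP labels its outputs as covering all AEs, so label and content agree. Unrelated AEs are not a readable endpoint. All AEs are listed by subject with dates as collected, so the few events concerned can be found by hand. This stands, and it keeps the point minor. It does not correct the table totals.

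The second defence is that silence is not an outcome. SAP 2.1.2 puts table formats in a companion document, the overall summary is not limited to its listed rows, and parts of Protocol 9.6 and of SAP 1.5 and 2.1.3 are blacked out. A restriction could sit there. This also stands, so the claim covers only the readable text.

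The third concerns the lips. The readable protocol goes from 7.1.6 to 7.4, and many eligibility criteria are redacted. The hidden criteria may exclude abnormal lips at baseline, in which case nothing is lost. The visible ones already exclude previous lip surgery, piercing, tattoo and facial trauma. Baseline frequencies can be set beside those at follow-up, and some new findings may be recorded as AEs under Protocol 7.1.1.2. All of this makes the size of the lip point unknown. It does not give the tables a within-subject comparison.

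A reader might infer more than the documents support:

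- **That the SAP departs from the protocol.** It does not, since neither sets an onset limit.
- **That AEs of screen failures are counted.** They are not, because the Safety population contains treated subjects only.
- **That the related-AE results are contaminated.** The causality definition prevents this.

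**Conclusion.** The point holds as a minor, cheap improvement. On the readable text, AEs of treated subjects with onset before the first injection would count in three summaries, and the term treatment-emergent is assigned but never used. The time shares in step 1 follow from the visit schedule. The event and subject counts rest on an assumed constant rate and a common screening interval, and the upper figures need all 50 subjects to wait the full 30 days. Most realistic combinations give less than one subject changing class. The readable safety endpoint, related AEs (Protocol 2.1.1), and the diary tables (SAP 2.5.3) are essentially unaffected.

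The lip tables cannot identify new or worsened findings if any subject is abnormal at baseline. Whether that will occur cannot be judged from the documents.

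**What to change.** In SAP 2.5.2:

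- Define a treatment-emergent AE as one with onset on or after the date of first injection.
- Keep the existing rule for completely missing start dates.
- Treat an AE with a partial start date as treatment-emergent unless the known date parts or the stop date show that it began or ended before the first injection. The existing imputation rules serve only days to onset and duration, so they do not settle this.
- Count Day 1 events as treatment-emergent unless the record shows that they were present before injection. The AE fields in Protocol 7.1.1.2 list a start date but no time.
- Count worsening when it is recorded as a new AE with its own start date.
- Base the all-AE, unrelated-AE and overall summaries on this definition, and show pre-treatment AEs separately.

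In SAP 2.5.4, add for each lip and visit either a shift from baseline or the number and percentage of subjects with a new or worsened finding.

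The cost is SAP wording, a few extra table layouts and slightly smaller AE totals. No new assessment is needed.
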